Protocol Title: Translational Investigation of Growth and Everyday Routines in Kids (**TIGER Kids**)

Principal Investigator: [name], MPP

Medical Investigator: [name]

Co-Investigators: [name], [name], PhD, [name], [name], RD, LDN

Protocol Version Date: 3/1/2021

Purpose and Objectives

Project Summary

Increasing physical activity and reducing sedentary behavior are key recommendations of the *Dietary Guidelines for Americans* as a way to balance calories to manage healthy weight. However, few youth meet recommended levels of physical activity, and interventions to increase physical activity often have low adherence and high drop-out rates. Furthermore, health behaviors may be particularly compromised in children with severe obesity, which is the fastest growing sub-category of obesity. Severe obesity affects three times more African American children than White children.1

Precision medicine is a transformative approach to change health behaviors that considers individual characteristics and environmental context. Our interdisciplinary team at Pennington Biomedical Research Center will establish a prospective pediatric cohort to identify intervention targets based on the location, timing, barriers, and facilitators of current physical activity and sedentary behavior in a child's day. Examining activity profiles and contexts by obesity status and race will allow interventions to be further tailored for high risk groups. We will accomplish the project's aims by conducting a prospective examination of up to 345 African American and White girls and boys aged 10 to 16 years, including approximately 50% who are classified as severely obese. We will use state-of-the-art technology including accelerometry to quantify physical activity, magnetic resonance imaging to quantify fat accumulation, and global positioning system (GPS) information and ecological momentary assessment to identify environmental and socio-emotional barriers and facilitators. This project will identify opportunities in a child's day to naturally integrate physical activity and reduce sedentary behavior to achieve the overall goal of creating actionable strategies to improve health.

Study Objectives

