The Pennington Biomedical recruitment core will execute a plan to advertise through branches of the public library system, seek the support of community leaders, issue personal appeals through social organizations, place advertisements in places of congregation (i.e. libraries, churches), and conduct direct mailings, as well as advertisements via newspaper, radio, and television. Our recruitment plan is based on strategies that have resulted in investigators successfully reaching their recruitment goals: 1023 children and adolescents for cross-sectional obesity screening studies (Investigator [name])₁₆ and 1043 children and adolescents into physical activity and dietary interventions (Project Lead [name] and Investigator [name]).⁷⁸⁻⁸¹ Baton Rouge area has an estimated 2013 population of 445,277 and almost 46% of the population is African American.⁸² Even with anticipated loss to follow-up, we will have sufficient power in overall logistic regression analyses.

Recruitment will begin in the spring of 2016 and is expected to end in the spring of 2018.

Study Timeline

Participants will be enrolled on a continual basis over the course of 24 months. Participation in the study will last approximately 2 years. It is estimated that the investigators will complete primary analysis by December 2019. The study timeline is reported in **Table 1**.

		2016		2017				2018				2019		
	Q2	Q3	Q4	Q1	Q2	Q3	Q4	Q1	Q2	Q3	Q4	Q1	Q2	Q3
Personnel Training														
Participant Recruitment														
Baseline Testing, Y0														
Follow Up Testing, Y2														
Data Management														
Data Analysis Y0														
Paper Writing &														
Submission, Y0														
Data Analysis Y2														
Paper Writing &														
Submission, Y2														

Table 1. Study Timeline

Procedures Involved

Study Design

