We will conduct a prospective epidemiological study to determine the effect of severe obesity on physical activity, sedentary behavior, and cardiometabolic risk factors among African American and White children and adolescents. Physical activity, sedentary behavior, cardiometabolic risk factors, and body composition will be assessed in each participant using gold standard, objective measures, with the first assessment (Year 0) in 2016-17 and the second assessment (Year 2) in 2018-19. We previously observed that children's physical activity and other health behaviors vary throughout the year based on school term versus school holiday.⁶⁰ Therefore, each child's Year 0 and Year 2 clinic visits will be scheduled at a consistent time of year to protect against changes due to the child being in school term or on a school holiday. Furthermore, we will use a scheduled enrollment to ensure that clinic visits are representative of both school term and school holidays.

Following an initial recruitment telephone screen or web-screen (followed by a telephone screen) to assess initial eligibility criteria, eligible participants will be scheduled for their Orientation visit at PBRC with their parent or legally authorized representative where participants will be formally oriented to the study by receiving detailed information on the purposes, goals, procedures, participant flow, and study timeline. Staff will obtain signed informed consent and child assent before participants take part in any of the study-related procedures. Participants will be given the GPS and accelerometer devices as well as instructions on how to wear them for the next week. Participants will also be given the EMA application on their personal cell phones or a provided mobile device along with instructions on how to respond to the prompts for the next week. Participants will be introduced to the ASA-24 dietary intake tool and provided instructions on how to complete two separate recalls from their home computer prior to the Year 0 clinic visit. Participants and parents may be asked to complete surveys on the devices while waiting. At the conclusion of the Orientation. Parents may receive reminders from staff for all tasks required of participants between orientation and Year 0.

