Participants will be fasting at the Year 0 visit. Measurements including anthropometry, blood draw, urine pregnancy test, body composition, dietary intake, activity monitor tracking equipment collection, and all remaining surveys will take place during the clinic visits. Participants must be accompanied by a parent or legally authorized representative at the clinic visits.

Approximately 10 days prior to the Year 2 visit, participants will pick up an accelerometer and GPS device to wear for 7 days and return at the Year 2 clinic visit. Participants will also be given instructions on how to complete two trials of the ASA-24 dietary intake tool from their home computer prior to the Year 2 clinic visit. Participants will return to clinic approximately 2 years (+/- 6 months) after their Year 0 visit for a Year 2 visit, in which all procedures collected during Year 0 will be repeated. **Table 2** includes a list of all measurements occurring at both visits. Parents may receive reminders from staff for all tasks required of participants between orientation and Year 2.

Measurements

	Orientation	Year 0	Year 2
Informed consent/assent	Х		
Anthropometry (Height, weight, waist size)		Х	Х
Blood Pressure		Х	Х
Body Composition (DXA, MRI)		Х	Х
Blood Draw		Х	Х
Urine Pregnancy Test (eligible females only)		Х	Х
Dietary Intake (ASA-24)		Х	Х
Family environment surveys		Х	Х
Neighborhood environment surveys		Х	Х
Body image and mood surveys		Х	Х
Global Positioning System (GPS)	7-days		7-days
Physical Activity (Actigraph GT3X+)	7-days		7-days
Ecological momentary assessment (eMA)	7-days		

Table 2. Study procedures

Description of tests and procedures

Anthropometry

Weight- Anthropometry will be measured to the nearest 0.1 cm (0.1 kg for weight). All measures are taken twice with the analyzed value being the average of both measurements. If the measures differ by greater than 0.5 units, a third measurement will be taken to replace the discrepant value. Participants wear only a hospital gown and undergarments while being weighed.

Height- Standing height will be measured using a Harpenden stadiometer (Holtain Limited, Crymych, UK). Participants will remove shoes, stand upright with heels and back against the stadiometer, inhale, and hold breath while an assessor provides traction to align the participant's head along the Frankfort Horizontal Plane during measurement. Weight will be measured using a Michelli GSE 460 scale (G.T. Michelli Co., Baton Rouge, LA).

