- Furman W & Buhrmester D. Children's perceptions of the qualities of sibling relationships. Child Development 1985;56(2):448-461.

mHealth Weight Management Program Acceptability Survey

Parents will complete a survey assessing program acceptability for an mHealth weight management program that teaches the parent and child dietary, physical activity, and behavioral change strategies.

Cyber Cycling Lifestyle Program Acceptability Survey

Parents will complete a survey via REDCap assessing acceptability for an exercise and healthy eating program for adolescents and young adults.

COVID-19 Survey

Parents will be asked to complete a survey related to the stay at home order that families were under due to the COVID-19 pandemic. The survey will be sent out via email using REDCap, where parents can click that they consent to completing the additional survey. Participants that have already completed the Year 2 visit will also receive the survey link, with an option to complete it. Parents will be asked to report on information related to their child's behavior habit changes, such as sleep, physical activity, diet and screen time.

Environmental Assessment and Analysis

Neighborhood environment

A participant's neighborhood will be defined as the 3/4-mile street network buffers around each child's residence (walkable distance from home), and neighborhood features will be enumerated within the buffers (see Colabianchi et al., 2014 as an example).⁹² Physical activity patterns will be characterized according to whether the physical activity occurs within 3/4-mile of the child's residence or not. As a point of comparison, the secondary definition of neighborhood environment will be the Census Block Group (BG) in which he/she resides. This definition has been used in other recent work assessing environmental influences on children's physical activity^{93,94} and is expected to be a good scale on which to measure the influence of neighborhood disorder and social processes.⁹³

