Analyses to test Hypothesis 2 will be conducted using a series of linear regression models (i.e. linear mixed effects models). Based on difference score between Years 0 and 2 for total body fat, the group will be divided into two dichotomous groups using percentiles: high fat gainer (HFG) and low fat gainer (LFG). These variables will be used to predict changes in physical activity, sedentary behavior, and each cardiometabolic risk factor in linear mixed effect models. Covariates will include age, sex, dietary intake, and race. School term vs. school holiday will be considered as an additional covariate if time of year is significantly associated with the independent and dependent variables. Secondary analysis will use MRI and DXA as covariates in the model (namely the visceral, trunk, and total body fat). As previously reported, variable select criteria (including LASSO and support vector machine) will be used to determine which combination of these variables best explains the variance in the data. The full model will enable the comparison the accumulation of imaging-based body composition measures vs. BMIz alone and their associations with change in physical activity, sedentary behavior, and cardiometabolic risk factors in children. Finally, there are no standard accepted definitions of pediatric severe obesity to dichotomize participants based on MRI or DXA measures of body fat. Therefore, receiver operating characteristic curves will be created to estimate the value at which visceral, trunk, and body fat best correspond with the BMI definition of severe obesity (i.e. $BMI \ge 120\%$ of the 95th percentile1). Clinically relevant cut-points of severe obesity based on total, trunk, and visceral body fat will be established among this diverse cohort of adolescents.

Power analysis

Objective 1:

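### Some Year 2 visits can fall after the COVID-19 stay-at-home order, and no Objective 1 or 2 change model has a term for it

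*Combined protocol and SAP*

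**What the plan says.** The document is headed "Protocol Version Date: 3/1/2021". Its COVID-19 Survey section describes "a survey related to the stay at home order that families were under due to the COVID-19 pandemic", so the order is already past. It continues: "Participants that have already completed the Year 2 visit will also receive the survey link, with an option to complete it". The survey asks about changes in the child's sleep, physical activity, diet and screen time.

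On timing, Recruitment Methods says: "Recruitment will begin in the spring of 2016 and is expected to end in the spring of 2018". Study Design puts the return visit "approximately 2 years (+/- 6 months) after their Year 0 visit", while also placing "the second assessment (Year 2) in 2018-19". Study Timeline expects the primary analysis by December 2019. Table 7 sets cumulative recruitment goals of 310 by September 2017 and 340 by December 2017.

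On analysis, the Objective 1 and Objective 2 sections each list age, sex, dietary intake and race as covariates. The only time-related term is conditional: "School term vs. school holiday will be considered as an additional covariate if time of year is significantly associated" with the independent and dependent variables. No analysis uses the COVID-19 survey, and no contingency section mentions the pandemic.

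**The concern.** The Objective 1 primary outcome is the Year 2 minus Year 0 change in accelerometer-measured sedentary minutes. A stay-at-home order could plausibly move that outcome directly. Study Design already treats school attendance as a threat to comparability: each child is to be seen at the same time of year at both visits. That controls season within a child. It does not balance calendar period between obesity groups, and a term-versus-holiday covariate does not describe closure or remote schooling.

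Two things are at stake. If the shift is shared equally, the contrast is less precise. If post-order visits are unevenly spread over the obesity groups, or the shift differs by obesity status, part of the pandemic effect is read as an obesity effect. Objective 2 has a further exposure: high fat gainers (HFG) and low fat gainers (LFG) are defined by fat change over the same interval as the outcome, so the order could affect both sides of that association.

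**Working it through.** **1. The plan's own figure.** Table 5, last row: difference 24 min/day, SD of change 69.6, minimum N 266. A two-sample t-test with 133 per group and two-sided 5% (sidedness is not stated; two-sided assumed) gives power 80.0%, so 266 reproduces. At the cap of 345 with 25% dropout there are 345 × 0.75 = 258.75 completers, or 129.4 per group, and power is 78.9%. This is the baseline below.

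**2. How many visits could be affected.** The documents do not date the order; about March 2020 is assumed.
- Outer limit from the text: spring 2018 + 30 months = about autumn 2020.
- From Table 7: September 2017 + 30 months = March 2020. Only children enrolled after September 2017 could be seen after the order within the window: (340 − 310)/340 = 8.8%, or 35/345 = 10.1% if the last five enrol in early 2018.
- At exactly 24 months, the December 2017 goal gives December 2019, before the assumed date.

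So about 10% is a ceiling on planned accrual. Actual accrual is not given, and late accrual would raise it.

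**3. Equal exposure, common shift.** Let D be the shift in min/day and p the affected share in both groups. The contrast is unbiased, and SD = √(69.6² + p(1 − p)D²). With p = 0.10 and 129.4 per group:

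| D (assumed) | SD | Power for 24 min/day |
|---|---|---|
| 0 | 69.6 | 78.9% |
| 30 | 70.2 | 78.2% |
| 60 | 71.9 | 76.3% |
| 90 | 74.7 | 73.1% |

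**4. Unequal exposure.** Bias = D × (p_SO − p_NSO). A 10-point imbalance gives 0.10 × 30 = 3 to 0.10 × 90 = 9 min/day, or 12.5% to 37.5% of the 24 min/day target. The standard error of the contrast is 69.6 × √(2/129.4) = 8.65. With no true difference, a bias of 3 raises the two-sided 5% error to about 6%, and a bias of 9 raises it to about 18%.

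**5. Unequal effect.** If the shift is 20 min/day larger in SO and 10% of each group is affected, the contrast moves by 0.10 × 20 = 2 min/day even with balanced timing.

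**6. Objective 2.** Table 6 targets 8.4 min/day. The same 3 to 9 min/day would be 3/8.4 = 36% to 9/8.4 = 107% of it, if post-order shares differed by 10 points between HFG and LFG.

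**7. Cost of adjusting.** An indicator correlated with SO multiplies the variance of the contrast by 1/(1 − r²), where r² = (p_SO − p_NSO)²/[4p̄(1 − p̄)] and p̄ is the mean of the two shares. For 5% versus 15%, r² = 0.028, the factor is 1.03 and power is 77.8%. For 15% versus 35%, r² = 0.053, the factor is 1.06 and power is 76.7%.

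**The case against.** The strongest objection is that the primary comparison is between groups. A shift common to SO and NSO youth cancels and leaves only extra variance. A reader might infer from the missing term that the primary result necessarily mixes obesity with pandemic effects. The documents do not support that: they show neither uneven timing nor an effect that differs by obesity status. This objection stands in full for Objective 1. It carries less weight for Objective 2, where the order could drive both fat gain and sedentary change.

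A second objection is to size. Shares of 20% or 30% are tempting to assume, but Table 7 with the assumed order date supports about 10% at most, and scheduling at a consistent time of year favours visits near 24 months. This also stands, except that the goals are not actual accrual.

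Third, the survey text does not prove that accelerometer visits took place after the order; outstanding visits may never have happened. That is fair, and it is why the point is that visits can fall after the order.

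Finally, a reader might infer from the version date that the 2021 version introduced the survey and left the analysis untouched. Only one version is available, so this cannot be checked and the point does not rely on it.

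**Conclusion.** The gap is real but its consequence is conditional. The survey wording and the visit window indicate that some Year 2 visits can fall after the order, and the listed covariates do not account for it. With about 10% affected and a shift of 30 to 90 min/day, both assumptions, the loss for Objective 1 is modest: about 1 to 6 points of power. Bias arises only with uneven timing or an uneven effect, at 3 to 9 min/day per 10 points of imbalance. That would be material against 24 min/day and more so against 8.4 min/day. The order date, the number of visits affected and their split by obesity group are all absent from the documents, so no single corrected figure can be given. The change is worth making because it is cheap and settles in advance how these visits are handled.

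**What to change.** Add a fixed indicator for a Year 2 visit before or after the order date to every model that uses Year 2 or change data, without a significance condition, and state the date used. As a sensitivity analysis, test the indicator's interaction with SO (Objective 1) or HFG (Objective 2), because an additive indicator corrects uneven timing but not an uneven effect. Repeat the primary analysis on pre-order Year 2 visits only. Report the number of post-order visits by group.

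The cost is one covariate from visit dates that the study should already hold, the interaction test and one extra run. Precision falls by about 1 to 2 power points if timing is unbalanced as in step 7. The restricted run has fewer children: with 10% removed, power for 24 min/day is about 75%, so it should be read as support and not as a replacement.

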We will include adolescents aged 10 to 16 years. We selected this age range because adolescence is a developmental period of rapid fat gain and changes in activity patterns. By choosing the maximum age as 16 years at baseline, the children are likely to still live in Baton Rouge and attend high school at the second clinic visit (age 18 years), facilitating follow-up.

Inclusion Criteria:

- Age 10-16 years
- Body weight < 500 lbs.
- Ability to understand instructions and complete all study procedures

Exclusion Criteria:

- Pregnant
- On a restrictive diet due to illness
- Significant physical or mental disabilities that impede walking, wearing accelerometer or GPS, or responding to EMA.

In addition to the exclusion criteria listed above, participants who refuse to provide written assent, or whose parents or legally authorized representative refuse to sign an informed consent document, will be excluded from the study. Consent/assent will be obtained upon each participant's arrival at the PBRC Pediatric Research Clinic before participating in any study procedures. To further safeguard participant safety and internal validity of the study, inclusion and exclusion criteria will be reassessed by PBRC clinic staff following the completion of required assent/consent forms. The principal investigator and medical investigator have the right to withdraw a participant from the study at any point for any reason.

Number of Participants

We will identify and recruit up to 345 boys and girls aged 10 to 16 years. The sample will be screened on the telephone in attempt to achieve a comparable sex and race distribution. We will oversample for severely obese youth so they comprise approximately 50% of the sample (with the other 50% being distributed among normal weight, overweight, and obese status).

Recruitment Methods

Recruiting children for clinical studies is challenging, particularly those from high risk populations such as with severe obesity and from ethnic minority groups. However, we are confident we can recruit up to 345 children within 2 years. A key recruitment strategy will be to enroll participants who completed the WAIST Study.¹⁶ Of 423 initial participants who were assessed for the WAIST Study in 2010-11, 386 (91.3%) agreed to be re-contacted. Of these, 193 participants will meet the age criteria for the follow-up

Page 7 of 35

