BMIz- BMI percentile and BMIz will be calculated based on the participant's age, height, and weight using the CDC 2000 growth charts.⁶¹ Severe obesity will be categorized as $\geq 120\%$ of the 95th BMI percentile.¹⁵

Waist circumference - will be measured at the natural waist (halfway between inferior border of rib cage and superior aspect of iliac crest) with clothing moved out of the way.

Body composition

DXA- Total body fat and trunk fat will be assessed by whole-body DXA using a GE iDXA scanner (GE Medical Systems, Milwaukee, WI) to quantify total and regional body fat (including trunk fat).

DXA Instructions given to participant: This scan measures the amount of bone, muscle, and fat in your body. The scan will be performed using a whole-body scanner. You will be required to wear a hospital gown, to remove all metal-containing objects from your body, and to lie down on the table. You will be carefully positioned on the table, and your legs will be placed together using two Velcro straps. A scanner emitting low energy X-rays and a detector will pass along your body. You will be asked to remain completely still while the scan is in progress. The scan takes approximately ten minutes.

MRI - Visceral fat, i.e. visceral adipose tissue, will be assessed by water-fat shifting MRI using the General Electric Discovery 750w 3.0 Tesla (GE Medical Systems, Milwaukee, WI). IDEAL-IQ imaging technique will be used to generate water-only, fat-only, in-phase, and out-of-phase echoes in a single acquisition with a 20-second breath-hold. For female subjects ages 12 and above or females under the age of 12 who are menstruating as verbally confirmed by a parent or legal guardian, a negative urine pregnancy test will be required prior to DXA or MRI scans.

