The hypotheses will be tested using a series of generalized linear models with severe obesity as the independent variable. First, linear mixed effect models will be used to test for effects between BMIz and each dependent continuous variable (change in: min/day sedentary behavior, min/day MVPA, and each cardiometabolic risk factor). Next, logistic regression models will be used to determine the association between BMIz with the likelihood of not meeting recommended behaviors (i.e. top quartile of min/day of sedentary behavior; MVPA < 60 min/day) or being at elevated cardiometabolic risk. Finally, the cohort will be stratified into two groups based on obesity at Year 0: severely obese (SO) and not severely obese (NSO). Logistic regression models will be used to determine associations between SO (vs. NSO) and each dependent variable (i.e. change in: minutes/day sedentary time, minutes/day MVPA, and each continuous cardiometabolic risk factor). Covariates will include age, sex, dietary intake, and race. School

term vs. school holiday will be considered as an additional covariate if time of year is significantly associated with the independent and dependent variables.

Secondary analysis will use MRI and DXA as covariates in the model (namely the visceral, trunk, and total body fat). These measurements, along with BMIz, may be highly correlated. Various variable select criteria (including LASSO and support vector machine) will be used to determine which combination of these variables best explains the variance in the data. The full model will enable the comparison of imaging-based body composition measures vs. BMIz alone and their associations with physical activity, sedentary behavior, and cardiometabolic risk factors in children.

As exploratory analyses, dietary intake will be tested as a potential mediator to explain significant associations between the predictor variable (BMIz) on outcomes (physical activity, sedentary behavior, and cardiometabolic risk factors). Series of sequential models will be used to test each pathway using a path analysis model based on the Baron and Kenny causal steps for mediation.73,74

Objective 2:

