Analyses to test the hypotheses will be conducted using linear models. The primary independent variable will be BMIz and the dependent variable will be physical activity (MVPA). The c statistic will be evaluated to assess the contributions of BMIz and the environmental (or socio-emotional) factors to increase the accuracy in model-based prediction of events using data collected at Year 0, Year 2, and the changes between Years 0 and 2. Linear models will also be used to examine if there are changes in environmental or socio-emotional factors between Years 0 and 2. Finally, severe obesity (vs. all others) will be tested as a dichotomous variable with each environmental or socio-emotional factor to determine associations with physical activity. School term vs. school holiday will be considered as an additional covariate if time of year is significantly associated with the independent and dependent variables. For the models investigating environmental factors, the independent variables will include the family environment, park access and crime, perceived neighborhood environment, physical activity locations, and physical activity opportunities. Family environment subscales related to physical activity will initially be summed to create a single continuous score, with higher values indicating higher family support for physical activity. Additionally, the average minutes/day of MVPA will be summarized by location type. To examine socio-emotional factors, the independent variables will include body image, mood, and the data collected from the EMA including the three affect states (i.e. happy, stressed, energetic) and the social context of the activity (i.e. activity type and who was with the participant). For both the environmental and the socio-emotional factors, associations that are positively related to physical activity will be identified as facilitators of each, and inverse associations will be identified as barriers of each.

Contingencies

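### BMIz is the only continuous BMI exposure in the planned models, and it has reduced resolution within the severely obese half of the cohort

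*Combined protocol and SAP*

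**What the plan says.** Under the BMIz entry of the test descriptions, BMI percentile and BMIz are derived from the child's age, "height, and weight using the CDC 2000 growth charts". The same entry continues "Severe obesity will be categorized as" at or above 120% of the 95th percentile, so SO status is not set by a BMIz cut. Number of Participants says "We will oversample for severely obese youth so they comprise approximately 50% of the sample".

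Statistical Analysis, Objective 1, opens with "generalized linear models with severe obesity as the independent variable". The first model set then uses BMIz: "First, linear mixed effect models will be used to test for effects between BMIz and each dependent continuous variable". So does the second: "logistic regression models will be used to determine the association between BMIz with the likelihood of not meeting recommended behaviors". Only the last set compares SO with NSO. The exploratory mediation models take BMIz as predictor. For Objective 3, "The primary independent variable will be BMIz and the dependent variable will be physical activity (MVPA"), with severe obesity tested as a binary variable at the end.

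The secondary analyses of Objectives 1 and 2 are meant to compare "imaging-based body composition measures vs. BMIz alone". The plan contains no other continuous BMI scale, no extended z-score and no non-linear BMIz term.

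**The concern.** A chart z-score of LMS form transforms BMI by a power L and scales it by S. BMI is right-skewed, so L is negative, and z then has a finite ceiling. Large BMI differences high on the scale become small z differences, and the study recruits about half its children from that region.

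Two things are at stake. First, SO versus NSO is binary, so BMIz is the only BMI variable that could show a gradient among the severely obese, and it is weakest there. Second, BMIz is the yardstick for MRI and DXA. Measured fat can keep rising where BMIz has flattened, so imaging may appear to add to BMI when it adds only to a compressed version of BMI.

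**Working it through.** **The plan's own figure.** Table 5, last row: difference 24 min/day, SD 69.6, alpha 0.05 (taken as two-sided), 80% power, equal groups.

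n per group = 2 × (1.960 + 0.842)² × 69.6² / 24² = 2 × 7.85 × 8.41 ≈ 132.0, rounded up to 133, so 266 in total, as stated. The stated total of 334 is 133 × 1.25 = 166.25, rounded up to 167 per group. Whether 1.25 is the right dropout factor is a separate question. BMIz enters neither figure.

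**Inputs for the scale check.** From the documents: CDC 2000 charts, the 120% threshold, and about 50% severely obese. Assumed, because the documents give neither: L from -2.0 to -2.5 and S from 0.12 to 0.15.

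**Formula.** z = ((BMI/M)^L − 1)/(L·S). At the 95th percentile z = 1.645, so (P95/M)^L = 1 + 1.645·L·S. With r = BMI/P95:

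z(r) = (r^L × (1 + 1.645·L·S) − 1)/(L·S), with ceiling −1/(L·S).

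Example, L = -2.0 and S = 0.12: L·S = -0.24 and 1 + 1.645·L·S = 0.6052. Then z(0.8) = (1.5625 × 0.6052 − 1)/(−0.24) = 0.23 and z(1.2) = (0.6944 × 0.6052 − 1)/(−0.24) = 2.42, a step of 2.19.

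| L, S | 80–120% | 120–160% | 160–200% | Ceiling |
|---|---|---|---|---|
| -2.0, 0.12 | 2.19 | 0.77 | 0.35 | 4.17 |
| -2.0, 0.15 | 1.47 | 0.51 | 0.24 | 3.33 |
| -2.2, 0.13 | 1.79 | 0.58 | 0.26 | 3.50 |
| -2.5, 0.12 | 1.88 | 0.55 | 0.22 | 3.33 |
| -2.5, 0.14 | 1.35 | 0.39 | 0.16 | 2.86 |
| -2.5, 0.15 | 1.14 | 0.33 | 0.13 | 2.67 |

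The ratio of two steps depends on L alone, because S cancels:
- L = -2.0: (1.5625 − 0.6944)/(0.6944 − 0.3906) = 2.9 for the second step, and 0.8681/0.1406 = 6.2 for the third.
- L = -2.5: 1.1130/0.3251 = 3.4 and 1.1130/0.1320 = 8.4.

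**Where the BMIz variation lies.** With illustrative distributions (SO: r = 1.2 + gamma with shape 1.5 and scale 0.13; NSO: r uniform from 0.65 to 1.2), the SD of r is about the same in both groups, 0.15 to 0.16. On the BMIz scale, 52–56% of the variance lies between SO and NSO, 42–47% within NSO and 1–2% within SO.

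**Imaging comparison.** Simulated cohorts had 258 children (345 × 0.75, rounded down), half of them SO. The outcome was linear in r, and the imaging measure was r plus noise, so imaging added nothing by construction. At a nominal 5%, imaging was significant beyond BMIz in 28–39% of runs when the outcome correlation was 0.3, and in 71–87% when it was 0.5. Beyond percent of the 95th percentile it was significant in 4–6%. A second simulation of the same kind gave 26–82% against 4–5%. The exact rates depend on how closely imaging is assumed to follow BMI.

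**The case against.** The strongest reply is that the study's main contrast does not use BMIz. Hypotheses 1.A and 1.B concern severe obesity, Table 5 is powered on SO versus NSO, and that split is defined on percent of the 95th percentile. Objective 2's main exposure is change in total body fat. No hypothesis states a gradient within the severely obese. The imaging comparison is labelled secondary and mediation exploratory, and the Background already calls MRI and DXA more precise than BMIz. All of this stands, and it limits the weight of the point.

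A reader might infer that BMIz barely separates severely obese children. That is not supported. At one age and sex BMIz keeps their order, and under the illustrative distribution (with L from -1.5 to -3 and S from 0.11 to 0.15) its r-squared with percent of the 95th percentile within SO is 0.93–0.97. The loss grows when ages 10 to 16 and both sexes are pooled. If L and S vary across them, r-squared falls to about 0.65 or 0.30, depending on how widely they are assumed to vary. Age and sex as additive covariates would not fully correct a scale that differs by age and sex.

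A reader might also infer that a BMIz slope is driven mainly by the non-severe children. The variance split does not support that either: the largest share is the SO–NSO contrast itself. What remains is the 1–2% share within SO.

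The documents give no L, S or ceiling, so the size is conditional on the assumed range. The 6- to 8-fold figure applies only from 160% to 200%; the documents do not say how many children will be there, and in the illustration about 10% of the SO group exceed 160%. The artefact in the imaging comparison requires outcomes roughly linear in BMI, and nothing in the documents supports that shape over a levelling-off.

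**Conclusion.** The point holds as one of reduced resolution. For L from -2.0 to -2.5 and S from 0.12 to 0.15, an equal BMI step counts about 3 times less from 120% to 160% of the 95th percentile than from 80% to 120%, and about 6 to 8 times less from 160% to 200%. The ceiling is z = 2.7 to 4.2. The existence of a ceiling follows from negative L; its height rests on the assumed parameters.

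The BMIz models in Objectives 1 and 3 and the mediation analysis therefore say little about gradient within the severely obese. If outcomes are roughly linear in BMI, the imaging comparison can favour MRI and DXA for reasons of scale. A reader might take this as a threat to the primary comparison or the sample size. It is not: SO versus NSO, the 120% cut, Table 5 and N are untouched. This is a worthwhile, inexpensive improvement to the analysis plan and not a flaw in the study's main test.

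**What to change.** Pre-specify BMI as a continuous percent of the 95th percentile as the BMI exposure in the Objective 1 and Objective 3 models, the mediation models and the imaging comparisons of Objectives 1 and 2. Report BMIz alongside as a sensitivity analysis. Leave the SO/NSO definition as it is. Since Objective 1 names both severe obesity and BMIz as the exposure, state there which one is the main exposure.

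The new variable is already needed to assign SO status, so no extra data, visits or participants are required. The cost is wording, a little more analysis work, and slightly less direct comparability with earlier BMIz papers, which the sensitivity analysis largely restores. Keeping BMIz as the main scale and adding percent of the 95th percentile, or a non-linear BMIz term, as a sensitivity analysis would be a smaller step. It would leave the headline BMI benchmark for imaging on the compressed or transformed z scale.
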